Secondary Endpoints	
 (1) Number of eligible patients over a 1-year period (2) Percentage of eligible patients providing consent (3) Progressive or new venous or arterial thrombosis (4) Bleeding events by WHO grade (5) Platelet transfusions (6) PRBC transfusions (7) Transfusion related outcomes (8) Quality of life (FACT-Th18)
Type of control	Institutional standard of care
Trial Blinding	Unblinded
Treatment Groups	A: transfusion threshold of $30 \times 10^9/L$ B: transfusion threshold of $50 \times 10^9/L$
Treatment Schedule	Transfusions will be administered as needed (based upon randomized threshold) throughout a single period of treatment-related thrombocytopenia OR 30 days, whichever is shorter
Number of trial subjects	12
Estimated duration of trial	One year
Duration of Participation	≤ 63 days

ABBREVIATIONS

CT scan	Computed tomography scan
ATE	Arterial thromboembolism
HSCT	Hematopoietic Stem Cell Transplant
SCCA	Seattle Cancer Care Alliance
VTE	Venous thromboembolism
AML	Acute myeloid leukemia
ALL	Acute lymphocytic leukemia
CML	Chronic myeloid leukemia
CLL	Chronic lymphocytic leukemia
MDS	Myelodysplastic syndrome
WHO	World Health Organization
DIC	Disseminated intravascular coagulation
PT	Prothrombin time
PTT	Partial thromboplastin time
V/Q	Ventilation/perfusion scan
APL	Acute promyelocytic leukemia
HLA	Human leukocyte antigen

Contents

1.0 GENERAL INFORMATION	7
1.1 Protocol Title	7
1.2 Sponsor Information	7
1.3 Investigator Information	7
2.0 INTRODUCTION TO THE PROTOCOL	7
2.1 Background and Rationale	7
2.2 Clinical Data to Date	8
2.3 Transfusion Threshold Rationale	9
2.4 Risks/Benefits	9
3.0 OVERVIEW OF CLINICAL TRIAL	10
3.1 Study Objectives	10
3.1.1 Primary Objective	10
3.1.2 Secondary Objectives	10
3.2 Study Population	10
3.3 Study Design	10
3.3.1 Primary Endpoint	10
3.3.2 Secondary Endpoints	11
3.4 Estimated Accrual	11
3.5 Funding Source	11
4.0 SAFETY CONSIDERATIONS	11
4.1 Stopping Rules	11
5.0 SUBJECT ELIGIBILITY	11
5.1 Inclusion Criteria	11
5.2 Exclusion Criteria	12
6.0 Subject Registration	12
7.0 Treatment Plan	13
7.1 Treatment Plan Overview	13
7.2 Baseline/Pre-Treatment Assessment	13
7.3 Randomization	13
7.4 Administration of Transfusions	13
7.5 Concomitant Medication and Supportive Care Guidelines	14
7.5.1 Unfractionated heparin (UFH)	14

7.5.2 Low molecular weight heparin (LMWH)	14
7.5.3 Anticoagulation Dosing Modifications	14
7.6 Transfusion Delays/Modifications	14
7.7 Duration of Therapy	15

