Patients received a median of 6 transfusions over the 30 days following diagnosis, accompanied by both a financial cost and a drain on resources. While cost data were not collected as a part of this study, previous studies have demonstrated increased cost (as high as \$5700/patient in 2014) associated with the use of prophylactic platelet transfusions to target a platelet count of $10 \times 10^9/\text{L}$.⁷ The higher target of $50 \times 10^9/\text{L}$ utilized for most patients in our retrospective study would naturally cost considerably more, in terms of financial cost to the patients, infusion room time and transportation costs (outpatients), prolongation of hospital stays (inpatients) and burden on the finite resource of blood products.

Another relevant issue is that of platelet refractoriness, defined as repeated, inadequate response to platelet transfusions. Rates of platelet refractoriness may be as high as 21.6%

among inpatients requiring platelet transfusions, adding both to the complexity of caring for such patients, particularly if and when bleeding does occur, and to those additional costs mentioned above including monetary (increased mean hospitalization cost of \$66,000 in the year 2000) and resource utilization (17.8 additional units of platelets/patients).⁸

Furthermore, platelet refractoriness may be a sign of the bigger issue of alloimmunization (defined as platelet refractoriness due to antibodies against antigens found in >25% of platelet donors), a major issue among patients undergoing repeated cycles of chemotherapy or stem cell transplant, requiring long term platelet support. Alloimmunized patients require HLA-matched platelet units from matched/directed donors, adding further to the expense and stress on resources. This is a common problem, affecting approximately five patients on the combined leukemia and transplant services at any given time.

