3.3.2 Secondary Endpoints

1. Progressive or new VTE
2. Progressive or new ATE
3. Hemorrhagic events (WHO grade 2 or greater)
4. A composite of a, b and c.
5. Major bleeds (WHO grade 3 or 4)
6. Number of platelet transfusions per patient during the study period
7. Platelet transfusion related complications
 - a. transfusion reactions
 - b. alloimmunization
 - c. volume overload
8. Percent of days on which subjects are transfused (or transfusions are not given) in compliance with the threshold to which they were randomized

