7.3 Randomization

Randomization may be obtained after or up to 72 hours before the platelet count drops below $50 \times 10^9/L$, as long as the period of thrombocytopenia (platelet count $< 50 \times 10^9/L$ in the absence of platelet transfusion support) is anticipated to last for ≥ 5 days. Following randomization, patients will receive platelet transfusions on all days when the morning platelet count is below the threshold to which they have been randomized. Platelet counts should be checked according to standard of care (daily while inpatient, ≥ 3 times per week while outpatient).

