8.2.4 Number of platelet transfusions

Only transfusions administered during the study period will be included. Transfusions administered 'off protocol' or inappropriately while 'on protocol' will also be counted. Type (apheresis unit or pooled packs) and volume of transfusion will also be noted.

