8.2.5 Platelet transfusion related complications

Platelet transfusion reactions will be defined as any of the following (1) new onset fever, chills, hypoxia, urticarial rash or hemodynamic instability during or within 1-2 hours of administration of a transfusion with or without hemolysis (2) transfusion related lung injury (TRALI) defined as new onset dyspnea/tachypnea and hypoxia within 6 hours of transfusion, accompanied by bilateral pulmonary edema on imaging, with or without fever and hypotension.

Volume overload will be defined as evidence of edema (pulmonary, extremity or other dependent area) on exam and/or imaging, requiring treatment with diuretics and/or dialysis. Contribution of platelet transfusions to volume overload will be determined based on the clinical judgment of an investigator.

Alloimmunization will be defined as a combination of platelet refractoriness (as defined in section 7.6) accompanied by a panel reactive antibody result of >25%.

8.2.6 Percent of days on which subjects are transfused (or transfusions are not given) in compliance with the threshold to which they were randomized

Study staff will determine the appropriateness of transfusion management (in accordance with the protocol) each on-protocol day of the study period. The frequency with which transfusions are given despite a platelet count above the determined threshold (not including 72 hour temporary increases or procedures as outlined in section 7.6) will be documented, as will the frequency with which transfusions are not administered within 24 hours after a platelet count below the determined threshold.

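### The all-days compliance percent (secondary endpoint 8) gives credit for days on which both thresholds call for the same action, so it overstates adherence to the assigned threshold

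*Combined protocol and SAP*

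**What the plan says.** Section 3.3.2, item 8, lists as a secondary endpoint: "Percent of days on which subjects are transfused (or transfusions are not given) in compliance with the threshold to which they were randomized". Section 8.2.6 sets the denominator: "Study staff will determine the appropriateness of transfusion management (in accordance with the protocol) each on-protocol day of the study period". It also records two error frequencies. One is "The frequency with which transfusions are given despite a platelet count above the determined threshold", with the temporary increases and procedures of section 7.6 left out. The other is "the frequency with which transfusions are not administered within 24 hours after a platelet count below the determined threshold".

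The action being scored is set in section 7.3: "patients will receive platelet transfusions on all days when the morning platelet count is below the threshold to which they have been randomized". The thresholds are 30 and 50 x10^9/L. Section 7.4 bases the decision on the first count of the day. Section 7.7 keeps a patient on protocol until the count has stayed above 50 for three consecutive days without transfusion, or for 30 days from randomization if that is shorter.

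On background practice, section 2.2 says that most patients at this centre are managed at 50, and: "Patients received a median of 6 transfusions over the 30 days following diagnosis".

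**The concern.** Teams used to a threshold of 50 may go on using it for patients assigned to 30. Whether that happens is a main thing for a feasibility pilot to find out, and endpoint 8 is the measure that quantifies it. A day on which both arms require the same action says nothing about which threshold is in use, yet it enters the score as compliant.

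On-protocol status does not separate the two situations reliably. Section 8.2.4 foresees off-threshold transfusions in patients who are still on protocol: "Transfusions administered 'off protocol' or inappropriately while 'on protocol' will also be counted". Neither 7.7.1 nor 9.1 names off-threshold transfusion as a reason for leaving protocol.

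The Sample Size and Power part of section 13 says that compliance will be weighed in judging whether the full non-inferiority trial is feasible. If the contrast between thresholds was only partly delivered and the compliance figure hides this, the full trial could be planned on too large a contrast. In a non-inferiority comparison, drift of one arm towards the other's threshold pulls bleeding rates together and favours a finding of non-inferiority.

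**Working it through.** The plan gives no figure for this endpoint, so there is nothing to reproduce first.

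**Step 1: where the arms differ (sections 7.3 and 7.4).**
- First count below 30: both arms transfuse.
- First count 30 to <50: the 50 arm transfuses and the 30 arm does not.
- First count 50 or above: neither arm transfuses.

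Section 7.4 also allows some transfusions after a post-transfusion or clinically indicated repeat count. Section 8.2.6 does not say how these enter the daily score, and they are set aside here. Each such day scored as a deviation would lower the score by 1/T.

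**Step 2: score under complete crossover.** Let T be on-protocol days and D the days with a first count of 30 to <50. Managed consistently at the other threshold, a patient is non-compliant on the D days and compliant on the rest:

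all-days score = (T - D)/T = 1 - D/T

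score on the D days alone = 0/D = 0%

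This assumes a count every day, so the dilution is separate from the question of days without a count.

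**Step 3: inputs.**
- T = 30 is the maximum (7.7). T = 14 is a short case, from the two or more weeks of frequent transfusion described in 2.2. T = 21 is an assumed middle value. Shorter periods are possible, since 7.3 requires only that at least 5 days of thrombocytopenia be anticipated.
- D is not in the documents. For a 30-arm patient managed at 50, every discordant day is a transfusion day, so the historical median of 6 transfusions suggests D = 6 if all were given at 30 to <50 and on separate days. D = 3 assumes half were. Applying the 30-day median to 21 or 14 days is a further assumption.

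**Step 4: results, 30-arm patient managed at 50.**

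| Assumed D | T = 30 | T = 21 | T = 14 |
|---|---|---|---|
| 6 | 24/30 = 80% | 15/21 = 71% | 8/14 = 57% |
| 3 | 27/30 = 90% | 18/21 = 86% | 11/14 = 79% |

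These are not bounds. D = 1 of 30 gives 29/30 = 96.7%; D = 8 of 14 gives 6/14 = 42.9%; D = 12 of 14 gives 2/14 = 14.3%.

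**Step 5: recovery days.** When the period ends by recovery, up to three days above 50 are credited in either arm: 3/14 = 21% of the score for T = 14, and 3/21 = 14% for T = 21.

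**Step 6: the other direction.** For a 50-arm patient managed at 30, the formula is the same, but the D days are untransfused days. The median of 6 transfusions does not inform D, and the documents give no other figure.

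**The case against.** The strongest reply is that the plan already exposes crossover. A 30-arm patient managed at 50 appears in the first error frequency of 8.2.6. Appendix 2 records the daily platelet count, and the threshold in use with the reason for any deviation. Transfusions per patient are reported, and 3.1.2 lists the degree to which platelet targets are achieved. Section 7.6 breaks randomization when a raised threshold for minor bleeding is needed beyond 72 hours or on three or more occasions, and 9.1.4 leaves exit to the investigator's discretion.

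Much of this stands: a careful reader of all these outputs could see systematic crossover. What is missing is the denominator. Six above-threshold transfusions in 30 days look like a 6/30 = 20% error rate when adherence on the days that mattered was 0%.

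A reader might infer that a patient in full crossover would pass the pilot's 70% feasibility criterion. The documents do not support that. The 70% appears only in the synopsis, without a unit. The endpoints part of section 13.2 sends primary compliance to 3.3.1, which counts patients on protocol at the end of the study period, and section 8.1 (Primary Endpoint) also speaks of a proportion of patients. On that reading 0.70 x 12 = 8.4, so at least 9 of 12 patients. Endpoint 8 has no pass mark.

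A reader might also take 57% to 90% as the range of scores under crossover. It is not. The median of 6 is not a ceiling, the cohort was mostly but not wholly managed at 50, and only one direction of crossover is illustrated.

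**Conclusion.** The point holds as a defect in how endpoint 8 is constructed. The all-days percent credits days that cannot tell the arms apart, so it overstates adherence to the assigned threshold. The structure follows from 7.3, 7.4 and 8.2.6 and needs no outside figure. The size does need an assumption, because the distribution of counts between 30 and 50 is not given. Under D = 3 to 6, a 30-arm patient managed entirely at 50 can still show a high compliance figure, while a larger D would make the crossover visible in the all-days percent.

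It would go too far to say that complete crossover would necessarily be reported as acceptable compliance, since the error frequencies and recorded thresholds partly reveal it. The consequence is limited: this is a descriptive secondary endpoint in a pilot of about 12 patients, with no decision rule of its own. It still matters, because compliance is to inform the design of the full trial.

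**What to change.** In 8.2.6 and 3.3.2 item 8, add a second measure, reported by arm: the percent of days with a first count of 30 to <50 x10^9/L that were managed according to the assigned threshold, excluding the temporary increases of 7.6. Give the number of such days and of patients contributing them. Use this measure when judging whether the contrast between thresholds was delivered. A patient managed throughout at the other threshold then scores 0%, and one managed as assigned scores 100%, whatever D and T are.

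Keep the all-days percent and both error frequencies beside it. The added measure does not see missed transfusions below 30 or transfusions at 50 or above, both of which are real non-compliance.

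State the unit of the synopsis 70%. If it is meant as a percent of days, apply it to the 30 to <50 measure.

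The cost is wording and one extra tabulation, because Appendix 2 already collects daily counts, thresholds and transfusions. The downside is fewer scored days per patient, and a patient with no day at 30 to <50 contributes none. No transfusion or anticoagulation rule changes.

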8.1 On-Study Clinical Evaluations

Targeted history and physical exam, bleeding diaries and FACT-Th18 questionnaires (Appendix 4) will be conducted in the manner outlined below. Laboratory studies will be conducted per standard of care in this institution, which is a minimum of three times per week.

8.1.1 Inpatient On-Study Visits

While inpatient at the University of Washington Medical Center, patients will be seen three times per seven-day period, visits should be as close to every other day as possible and no more than 3 days apart.

8.1.2 Outpatient On-Study Visits

While outpatients, being followed at the Seattle Cancer Care Alliance, patients will be seen weekly on the same day as other routinely scheduled care (eg clinic visits, nursing assessments, infusion center visits). Visits should be as close to every seven days as possible and no more than 12 days apart.

8.1.3 On-Study Visit Procedures

The following tests and procedures are completed, although not all tests may be done at each visit.

- Targeted history for symptoms of bleeding or thrombosis
- Targeted physical exam for symptoms of bleeding or thrombosis, volume overload
- Most recent complete blood counts (assessed within one day)

- FACT-Th18 Questionnaire (Appendix 5) will be completed weekly
- Bleeding diary (Appendix 4) will be reviewed at each visit and collected weekly
- Additional chart review including but not limited to documentation of suspected hemorrhage, thrombosis and/or transfusion reaction, transfusion administration, vascular imaging data, administration of anticoagulants, antiplatelet agents, antifibrinolytic or other pro-coagulant therapies and/or diuretics, dialysis for volume overload.

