**FRED HUTCHINSON CANCER RESEARCH CENTER
UNIVERSITY OF WASHINGTON SCHOOL OF MEDICINE**

Current version: 3

Previous version:2

**Management of Venous Thromboembolic Events (VTE) in Patients
with Hematologic Disorders and Treatment-Induced
Thrombocytopenia: a Pilot Study**

Principal Investigator:

- [name], Professor, UW [contact])

Co-Investigators at FHCRC/UW

- [name] PhD, Assistant Member, FHCRC, Professor, UW [contact])
- [name], Professor, UW [contact])

Study Coordinator FHCRC:

- [name], Clinical Research Coordinator SCCA [contact]);
email:[contact]

Data Coordinator FHCRC:

- [name], Clinical Research Coordinator,, SCCA [contact]); email:
[contact]

Emergency Phone (24 hours):

For non-transplant patients: Call the paging operator at the University of Washington Medical Center at [contact], and ask for the Fellow on call for Hematology/Oncology.

For transplant patients: Call the 8NE front desk at the University of Washington Medical Center at [contact], and ask for the triaging provider covering the transplant service.

PROTOCOL SYNOPSIS

Protocol Title	Management of Venous Thromboembolic Events (VTE) in Patients with Hematologic Disorders and Treatment-Induced Thrombocytopenia: a Pilot Study
Protocol Number	
Protocol Sponsor	None
Trial Phase	Pilot
Trial Type	Noninferiority
Clinical Indication	Management of treatment-induced thrombocytopenia during anticoagulation
Study Objectives	
 1) Determine feasibility of an RCT comparing platelet transfusion thresholds of 30×10^9 vs 50×10^9 in anticoagulated patients 2) Report bleeding outcomes as they would be in a full trial 3) Report patient reported outcomes as they would be in a full trial
Study Design	Randomized controlled trial
Population	Adult patients with moderate to severe thrombocytopenia related to the treatment of a hematologic malignancy and/or stem cell transplant for a hematologic disorder who require anticoagulation for a recently diagnosed venous thrombosis.
Primary Endpoints	(1) Feasibility defined as ≥ 12 patients enrolled over a 1-year period and (2) $\geq 70\%$ compliance with study-determined transfusion threshold at the time of count recovery

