7.2 Baseline/Pre-Treatment Assessment

The following procedures will be obtained at baseline before randomization to establish trial eligibility and allow patient characterization. Results of tests and/or procedures conducted as per standard of care will be used to determine study eligibility.

- Medical history including disease and treatment specifics of both the hematologic malignancy and the venous thrombosis, history of bleeding and anti-thrombotic therapy including anticoagulation and antiplatelet agents.
- Targeted physical exam for evidence of bleeding, thrombosis and volume status
- Most recent complete blood counts (assessed within 3 days of study day 0)
- Most recent coagulation assays, including PT, PTT (within one week of study day 0) and fibrinogen (if available).
- CT scan, V/Q scan, Doppler ultrasound or other appropriate diagnostic modality to document VTE diagnosis.

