7.7 Duration of Therapy

Patients will remain on protocol until (1) the platelet count spontaneously recovers to $>50 \times 10^9$ for three consecutive days, in the absence of transfusions or (2) for a maximum of 30 days after the date of randomization, whichever is shorter. The study period is defined as the period between the first on-study day (post-randomization) with platelet count $<50 \times 10^9$ and either of these endpoints regardless of whether the patient receives transfusions according to protocol or not. Following conclusion of the study period, transfusion thresholds will be determined by each subject's primary provider.

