8.1.4 End of Treatment (EOT) Visit Schedule and Procedures

This visit will occur on the first outpatient visit following platelet count recovery (within one week) or within three days of count recovery in the inpatient setting. Procedures will include a verbal history of any bleeding or thrombotic symptoms, focused physical exam for evidence of either, FACT-Th18 questionnaire and results of the most recent complete blood count ordered by the patient's provider.

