13.2 Primary/Secondary Endpoints/Hypotheses and Analytical Methods

The primary endpoints of this study are (1) enrollment and (2) compliance. Enrollment will be described at the end of a 12-month period and (2) compliance will be evaluated as described in section 3.3.1. The secondary endpoints described in sections 3.3.2 will also be reported and analyzed with descriptive statistics only. This trial is not powered to detect statistically significant differences between the study arms for these clinically important endpoints. Rather, the primary goal is to establish feasibility for enrollment into a formal trial.

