Appendix 1: Trial Screening, Entry, Randomization, Treatment and Monitoring Flow Diagram

Appendix 2: Data Collection Throughout the Study

Study Period	Data Collection
Screening	Age, gender Diagnosis and treatment 6 month bleeding/thrombosis history (including active bleeding) If ineligible: reason for ineligibility
Consent	If consent refused: reason for refusal
Enrollment	Malignancy diagnosis and treatment Lifetime bleeding/thrombosis history Transfusion history Anticoagulation plan (per managing physician) Weight, CBC, metabolic panel
Active management	Daily platelet count Platelet transfusion threshold (and reason for deviation if present) Transfusion data (product, number, response when available) Daily bleeding assessment VTE symptom assessment Anticoagulation management (missed or held doses)
30 Day Follow-up	Platelet count Current platelet threshold Current anticoagulation plan 30 day bleeding/thrombosis history

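### FACT-Th18 has no scheduled pre-randomization assessment, and its end-of-treatment form has no trigger for patients whose platelets have not recovered by day 30

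*Combined protocol and SAP*

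**What the plan says.** The third synopsis objective is "Report patient reported outcomes as they would be in a full trial", and FACT-Th18 is the eighth synopsis secondary endpoint. Section 2.4 names better quality of life as a possible benefit of the lower threshold. The trial is unblinded.

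The schedule is spread over several sections:

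- **Before randomization (7.2).** "The following procedures will be obtained at baseline before randomization to establish trial eligibility and allow patient characterization". The list that follows covers history, targeted examination, blood counts, coagulation assays and imaging of the clot. FACT-Th18 is not on it.
- **On study (8.1.3).** "FACT-Th18 Questionnaire (Appendix 5) will be completed weekly".
- **End of treatment (8.1.4).** The visit includes FACT-Th18. Its timing is "This visit will occur on the first outpatient visit following platelet count recovery (within one week"; for inpatients it falls within three days of recovery.
- **Study period (7.7).** Patients stay on protocol until spontaneous recovery or "for a maximum of 30 days after the date of randomization, whichever is shorter".
- **Later follow-up (7.8).** Chart review, verbal history and, where appropriate, a brief examination. No questionnaire is listed.
- **Data collection table (Appendix 2).** The enrollment row has items such as "Lifetime bleeding/thrombosis history". FACT-Th18 appears in no row.
- **Analysis (13.2, Primary/Secondary Endpoints).** "The secondary endpoints described in sections 3.3.2 will also be reported and analyzed with descriptive statistics only". The list in 3.3.2 does not contain FACT-Th18.

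**The concern.** A full trial reporting a patient-reported outcome would normally show where each arm started. Here the first scheduled score follows randomization, when patient and staff know the threshold. Several Appendix 5 items ask about worry over bleeding and inconvenience from platelet transfusions, and knowledge of the arm could plausibly shift those answers from the first form onward. A difference present at entry then cannot be told apart from an early effect of the assigned threshold or of knowing it.

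The second gap is at the other end. Two events close the study period, but only one of them triggers the end-of-treatment form. The patients without a trigger are those with the longest thrombocytopenia, for whom transfusion burden is likely to matter most. If staff wait for a later recovery, the form is completed after the study period, when 7.7 returns the choice of threshold to the treating provider.

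A pilot is also where a full trial would learn the baseline completion rate, the spread of scores at entry and the correlation between baseline and follow-up. This schedule yields none of the three.

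**Working it through.** The plan gives no effect size, standard deviation or power for FACT-Th18, so there is no figure to reproduce. The check is a comparison of the schedule sections, followed by illustrative arithmetic.

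**Schedule**

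1. Baseline: 7.2 omits the form, and the first mention of its completion is under on-study evaluations. Hence there is no scheduled pre-randomization score.
2. During the study period: the weekly rule in 8.1.3 does not depend on recovery. Section 9.2 keeps patients who stop active treatment under observation to the earlier of recovery and day 30, unless they withdraw consent. A patient unrecovered at day 30 has about 30/7 = 4 whole weekly intervals, or 30/12 = 2 if every outpatient gap runs to the 12-day limit in 8.1.2.
3. End of period: 7.7 gives two closing events and 8.1.4 covers one. For closure at day 30 without recovery, no end-of-treatment form is defined, and 7.8 does not supply one.

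**Size of a chance difference at entry**

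Inputs: 12 patients (synopsis) randomized 1:1 (13.1), so about n = 6 per arm. Scores are in units of their own SD.

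- SE of the between-arm difference = √(1/6 + 1/6) = 0.58 SD.
- Probability that the difference exceeds 0.5 SD in either direction = 2 × [1 − Φ(0.5/0.577)] ≈ 0.39.

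**What a baseline could add to precision**

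The correlation r between baseline and follow-up is not in the documents. I assume 0.5 to 0.7 and equal variances.

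| Method | SE formula | r = 0.5 | r = 0.7 |
|---|---|---|---|
| Follow-up score only | √(2/6) | 0.58 SD | 0.58 SD |
| Change from baseline | √(2/6) × √(2(1 − r)) | 0.58 SD | 0.45 SD |
| Covariate adjustment | √(2/6) × √(1 − r²) | 0.50 SD | 0.41 SD |

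The variance reduction is 25% to 49% with covariate adjustment and 0% to 40% with change scores. The adjustment formula ignores the cost of estimating a slope from 12 patients, so the real gain would be somewhat smaller.

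**The case against.** The strongest reply is that this is a 12-patient feasibility pilot whose primary endpoints are enrollment and compliance, with secondary endpoints described only. Randomized arms can be described on follow-up scores without a baseline, and chance imbalance between arms of six is unavoidable. Even with covariate adjustment the SE stays at 0.41 to 0.50 SD. This stands: the case for a baseline here is description and preparation for the full trial, not inference.

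Several stronger readings are tempting, and the documents do not support them.

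- *Quality of life is lost for patients unrecovered at day 30.* It is not. Weekly forms continue, and with the 7-day recall in Appendix 5 a late weekly form covers much of the final week. Only the form labelled end of treatment lacks a time. Recovered patients' end-of-treatment forms also fall at or after the close of their study period.
- *Quality of life cannot be read as change at all.* Change from the first on-study score is available. That score follows randomization, though an early one may partly recall days before it.
- *Up to 12 days pass before the first outpatient score.* Section 8.1.2 sets a maximum gap between visits, not the time to the first form. Inpatients are seen three times a week.
- *Section 13.2 excludes FACT-Th18 from analysis.* It points to a list that omits the questionnaire, while the synopsis includes it. This is a listing inconsistency and says nothing about baseline.

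Appendix 2 is weak evidence by itself, since it omits FACT-Th18 even for active management, where 8.1.3 plainly schedules it. The point rests on 7.2. The Appendix 1 flow diagram is not readable in the text available; if it shows a baseline questionnaire, 7.2 should be brought into line with it.

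**Conclusion.** The point holds in two limited parts. First, no pre-randomization FACT-Th18 is scheduled, so neither change from a true baseline nor the comparability of the arms at entry can be described. Second, the end-of-treatment form is undefined for patients who close the study period at day 30 unrecovered, so a common end-of-period score is missing for them.

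The 0.58 SD figure and the chance of about 39% rest on 6 per arm and approximate normality. Any gain in precision rests on the assumed correlation and should not be the reason for the change. The reason is that the synopsis promises reporting at the standard of a full trial, and the present schedule falls short of that for very little saving. This is an inexpensive improvement to a secondary endpoint, not a threat to the trial's main conclusions.

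**What to change.** 1. Add FACT-Th18 to 7.2 and to the enrollment row of Appendix 2, completed after consent and before the arm is known. Add the weekly and end-of-treatment forms to Appendix 2 as well.
2. In 8.1.4, time the end-of-treatment questionnaire to the end of the study period as 7.7 defines it, so that day 30 without recovery also triggers it.
3. State in 13.2 that baseline and follow-up scores will be described by arm, with the number of forms completed at each time. If any between-arm comparison is shown, give a baseline-adjusted estimate; a raw change score gains nothing at a correlation of 0.5.
4. List FACT-Th18 in 3.3.2 so that it matches the synopsis.

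The cost is one extra 18-item form per patient, about 12 forms in all, plus wording changes. The downside is a small added burden around consent, when patients are dealing with a recent clot. No clinical rule changes.
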